14.7.1 Co-enrolment agreement form

In general we will encourage engagement in research projects other than the CLASSIC trial. Please, fill in the information of the trial to be evaluated as counterpart for co-enrolment with CLASSIC, and send it by e-mail to [contact].

Once we have received the information below, we will contact the principal/coordinating investigator of the trial and facilitate exchange of protocols and other relevant documents between the Management Committees. You will find a list of titles already considered for co-enrolment by clicking http://www.cric.nu/co-enrolment-list/

We have prepared the form for only one trial, but please feel free to copy as many forms as you need.

a. Official full/short title of the project:

b. Contact information of principal/coordinating investigator of the trial:

Name:

E-mail:

The CLASSIC trial protocol Page 65/82

14.8 Appendix 8. List of proposed sub-studies

- The effect of co-enrolment on the intervention effect in the CLASSIC trial
- The effect of restrictive fluid management on glycocalyx degradation a preplanned substudy of the CLASSIC trial
- Temporal changes in plasma lactate concentration in critically ill patients with septic shock treated with restrictive compared to standard fluid therapy a substudy to the CLASSIC trial

itself, as demonstrated by electron microscopy of ruthenium-red labeled rat myocardial capillaries. In vivo, the glycocalyx forms an even more substantial ESL, with thickness >1 mm. Figure 1a used with permission from van den Berg et al. (5)

(b) Pathological degradation of the glycocalyx/

ESL during critical illnesses (such as sepsis) causes not only local endothelial injury, but also releases biologically active heparan sulfate fragments

into the circulation that may influence signaling processes in an endocrine fashion. For simplicity, chondroitin sulfate and hyaluronic acid are not

shown. a4 and b4 refer to glycosidic bonds connecting constituent saccharides. Inset: structure of a heparan sulfate octasaccharide fragment,

demonstrating potential sites of sulfation within constituent disaccharide units.

Figure 1b used with permission from SAGE publishing open access (2).

It is possible that the endothelial dysfunction observed in septic patients is due to glycocalyx dysfunction. Moreover, inflammatory cytokines increase the secretion of angiopoietin-2 (Ang-2) from the endothelial cells (6), and Ang-2 has been shown to increase glycocalyx shedding (7). Ang-2 levels are associated with mortality in sepsis (8).

Degradation of the endothelial glycocalyx can either be proved directly by electron microscopy or indirectly by elevated levels of its degradation products; syndecan-1, heparan sulfate and hyaluronic acid. It has been shown to be degraded in different clinical situations, like exposure for endotoxins (9), infection (10), critical illness (11) and septic shock (12). It is also damaged by intravenous fluid bolus therapy(13) (14). In a septic mice model, the thickness of the glycocalyx significantly diminished during induced sepsis (15). High levels of Syndecan-1 has been suggested as a marker to identify

The CLASSIC trial protocol Page 68/82

patients at higher risk of negative effects of fluid therapy (11). In a study of patients in septic shock in the emergency department there was an association between fluid balance the first three hours and the levels of HA, but it is uncertain to what extent fluid therapy contributes to degradation of the glycocalyx. (10).

The aim of this study is to study the effect of restrictive fluid management compared to standard care on the levels of hyaluronan. We will also analyze the association between high hyaluronan, heparan sulfate, syndecan-1 TNFR, IL-6and Ang-2 levels at arrival to the ICU with fluid overload. Thus, we will explore the possibility of using degradation products of the glycocalyx as markers of patients with high risk to suffer from complications from fluid overload.

Method

This will be a sub-study in an RCT of restrictive fluid management in patients with septic shock, the CLASSIC trial, which is a continuation of the CLASSIC pilot trial(16). In the CLASSIC trial1554 patients will be randomized to restrictive or standard fluid therapy during the ICU stay. Blood samples will be drawn at T_0 (during the first hour after enrolment), T_1 (the first morning after inclusion) and T_2 (the second morning) and T_3 (at ICU discharge (within 24 hours before discharge)). We will collect blood samples for blood for RNA analyses, EDTA-plasma, Citrate-plasma and serum in four test tubes. Blood samples will be handled in accordance to the attached handling procedure (attachment 1). All samples will be kept in a research freezer at -80C until further analysis at one central laboratory. We aim to analyze markers of glycocalyx break-down products: heparan sulfate, syndecan-1, hyaluronic acid, IL-6, TNFR, Ang-2.

Outcomes

Study 1. The primary outcome is the difference in concentration of hyaluronan at the first morning after enrolment(T_1) in the restrictive group compared with the control group, adjusted for the T_0 values.

Secondary outcomes are associations between glycocalyx degradation product levels (heparan sulfate, syndecan-1, hyaluronic acid, IL-6, TNFR, Ang-2.) at arrival in the ICU and fluid balance after 24 and 72 hours in the ICU.

Statistical methods and sample size calculation

Baseline clinical and demographic data will be analyzed using chi-square or Fisher's exact test for categorical data, and the Wilcoxon rank-sum test for continuous data. The baseline and first follow-up measure of the concentration of hyaluronan will be modeled using a mixed effect linear model

The CLASSIC trial protocol Page 69/82

with a person specific random effect and an interaction between time of follow-up measure (interval since first measurement) and treatment group, the stratification variables for the randomization: hematological or metastatic cancer (Y/N) and trial site as fixed effects. Where biomarkers are normally, or log-normally distributed, mixed model analyses will be employed to analyze the pattern over time. Differences in the pattern of expression of each biomarker between the groups will be tested by the interaction of time and group in the model. Additional covariates will be added to adjust for treating center, illness severity (SAPS 3), cumulative fluid balance and comorbidities (Charlson comorbidity index).

A conservative sample size calculation reveals that with an assumed standard deviation of 29 ng/ml of hyaluronan concentration (established in previous comparable studies (10), a sample size of 200 would yield 80% to detect a group difference of 11.5 ng/l at T_1 . True power will be higher as the planned analysis also controls for baseline values, but as the exact size of this correlation is not known we restrict our self to the conservative sample size calculation. To account for drop-out or similar we will add a further 10% and therefore target a sample size of 220 equally distributed between the two groups.

We will use the Jakobsen-Lange adjustment to adjust for several secondary outcomes (17) where α_i for each outcome is α_i =0.05/((n+1)/2) which is an adjustment halfway between no adjustment and full Bonferroni adjustment with n being the number of co-primary outcomes and secondary outcomes respectively.

Importance

This study might elucidate the mechanism through which fluid therapy affects the glycocalyx.

Glycocalyx markers might also be able to identify patients at risk for fluid leakage and thus more complications from fluid therapy. This might be a way to personalize fluid therapy in septic patients.

References

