6.1 Experimental intervention

No IV fluids should be given unless one of the below extenuating circumstances occurs; in these cases, IV fluid may be given in measured amounts:

- In case of severe hypoperfusion or severe circulatory impairment defined by either:
 - Lactate 4 mmol/L or above
 - Mean arterial blood pressure below 50 mmHg (with or without vasopressor/inotrope)
 - Mottling beyond the kneecap (mottling score >2) OR
 - Urinary output less 0.1 mL/kg bodyweight/h, but only in the first 2 hrs after randomisation

A bolus of 250-500 ml of IV crystalloid solution may be given followed by re-evaluation. These criteria identify patients at increased risk of death [35, 36, 37], and were found feasible and not associated with harm in the CLASSIC pilot trial [5].

- In case of overt fluid losses (e.g. vomiting, large aspirates, diarrhoea, drain losses, bleeding or ascites tap) IV fluid may be given to correct for the loss, but not above the volume lost.
- In case the oral/enteral route for water or electrolyte solutions is contraindicated or has failed as judged by the clinical team, IV fluids may be given to:
 - Correct dehydration or electrolyte deficiencies.
 - Ensure a total fluid input of 1 L per 24 h (fluids with medications and nutrition counts as input).

IV fluids may be given as carrier for medication, but the volume should be reduced to the lowest possible volume for the given medication.

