A systematic review from 2016 by Vincent JL et al., which included 34 observational sepsis studies, showed that decrease in lactate concentration over time was consistently associated with lower mortality rates in all subgroups of patients (3). Hyperlactatemia is in clinical practice often thought to indicate that the human body is unable to uphold aerobic metabolism, due to tissue hypoxia and/or a deranged micro-circulation. This is often taken as an indication that a sufficient amount of resuscitation fluid has not yet been given to the patient. However, there are many other causes for hyperlactatemia, such as increased glycolysis, decreased clearance, and adrenergic stress response (4, 5).

In a Dutch multicenter randomized controlled trial from 2010 lactate-guided therapy in hyperlactatemia (albeit from various causes) reduced mortality, but interestingly the lactate levels did not differ significantly between the groups (6).

The current paradigm states that treatment with fluids decreases elevated concentrations of plasma lactate. Therefore, it is somewhat surprising that the post-hoc analysis of the Conservative versus Liberal Approach to fluid therapy of Septic Shock in Intensive Care (CLASSIC) feasibility trial (7)

The CLASSIC trial protocol Page 72/82

¹ Perioperative Medicine & Intensive Care, Karolinska University Hospital Huddinge, Sweden

² Department of Intensive Care, Rigshospitalet, University of Copenhagen, Copenhagen, Denmark.

³ Department of Anesthesia and Intensive care Medicine, Charles University Hospital Pilsen, Czech Republic

⁴ Department of Clinical Science and Education, Södersjukhuset, Karolinska Institutet, Stockholm, Sweden

showed no significant differences in plasma lactate levels between the two treatment groups even though there was >1 L difference in received fluids between the groups. The trial itself was not powered to investigate this outcome, but the finding is worth investigating in the main study.

Trial hypotheses and outcomes

The objective of this sub-study of the CLASSIC-trial is to use the randomization to either restrictive or standard fluid therapy to study temporal changes of lactate and time to normalization in patients with septic shock.

Research questions:

- 1. Does the lactate values differ between the two intervention groups in terms of
- a. Temporal changes in concentrations over time (based on all available plasma lactate analyses during the first 72 hours).

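### The glycocalyx sub-study adds cumulative fluid balance, which the intervention itself changes, to its between-group biomarker models and does not clearly exempt the hyaluronan model

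*Protocol*

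**What the plan says.** Protocol section 14.8.1.a gives its purpose as follows: "The aim of this study is to study the effect of restrictive fluid management compared to standard care on the levels of hyaluronan". For its main endpoint it names this contrast: "difference in concentration of hyaluronan at the first morning after enrolment(T_1) in the restrictive group compared with the control group, adjusted for the T_0 values".

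The statistical methods then run in this order:

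- The T0 and T1 hyaluronan values are modelled with a person-level random effect and a time-by-group interaction, plus "the stratification variables for the randomization: hematological or metastatic cancer (Y/N) and trial site as fixed effects".
- Mixed models follow for the course of the biomarkers over time, with this test: "Differences in the pattern of expression of each biomarker between the groups will be tested by the interaction of time and group in the model".
- The next sentence reads: "Additional covariates will be added to adjust for treating center, illness severity (SAPS 3), cumulative fluid balance and comorbidities (Charlson comorbidity index".

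That last sentence is unconditional. It does not say which model receives the covariates, over what period the balance is cumulated, whether it is one value per patient or is updated at each sampling time, or whether the adjusted model is exploratory.

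Three other places bear on the role of fluid. Section 6.1 instructs the restrictive arm: "No IV fluids should be given unless one of the below extenuating circumstances occurs; in these cases, IV fluid may be given in measured amounts". Section 14.8.1.b says that lactate did not differ significantly in the feasibility trial "even though there was >1 L difference in received fluids between the groups". The glycocalyx background says of the glycocalyx: "It is also damaged by intravenous fluid bolus therapy(13) (14".

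**The concern.** The documents themselves describe a chain: allocation changes fluid, and fluid is a proposed cause of glycocalyx damage. Cumulative fluid balance lies in the middle of that chain. Conditioning on it in a model of the randomised comparison has two consequences.

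First, the estimand changes. The stated aim is the total effect of the strategy on the marker. With balance held fixed, the group term estimates only the part that does not run through fluid. A true effect that works through fluid would be shrunk and could be reported as absent.

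Second, the comparison loses the protection of randomisation. Anything unmeasured that drives both balance and marker levels, such as evolving severity, can bias the group term.

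The form of the term decides whether this happens, and the plan leaves the form open.

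**Working it through.** **1. Which model?** The primary outcome names adjustment for T0, and the T0/T1 hyaluronan model lists cancer stratum and site. Fluid balance appears in neither place. The covariate sentence comes after the text has moved on to the pattern of each biomarker over time. Hyaluronic acid is on the list of markers to be analysed, so a hyaluronan pattern model over T0 to T3 is within reach of that sentence. The primary model is therefore not stated to be adjusted, but hyaluronan is not clearly exempt.

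**2. The plan's own figure.** Inputs from section 14.8.1.a: difference 11.5, SD 29, 200 patients (100 per arm), 80% power. Two-sided alpha of 0.05 is assumed, since no sidedness is given.

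- n per arm = 2 × (1.96 + 0.84)² × 29² / 11.5² ≈ 100, so 200 in total. This agrees.
- SE = 29 × √(2/100) = 4.10. Power = Φ(11.5/4.10 − 1.96) = Φ(0.84) = 80.1%.

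The SD is printed in ng/ml and the difference in ng/l. The figure reproduces only if both are in the same unit, so one unit looks like a typing error.

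**3. Illustration: the T1 comparison with balance added.** Two quantities are not in the documents and are assumed: m, the share of the effect acting through fluid balance (0 to 1), and d, the separation of the groups in balance, in SD units. The residual SD is held at 29.

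- Effect left in the group term = (1 − m) × 11.5.
- Variance inflation = 1 + (d/2)². At d = 0.5 this is 1.0625, so SE = 4.10 × √1.0625 = 4.23.
- Power = Φ((1 − m) × 11.5 / SE − 1.96).

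| m | Effect left | Power at d = 0.5 |
|---|---|---|
| 0 | 11.5 | 78% |
| 0.25 | 8.6 | 53% |
| 0.5 | 5.75 | 27% |
| 0.75 | 2.9 | 10% |
| 1 | 0 | none (2.5% in that tail) |

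At m = 0.5, power is 29% with d = 0 (SE 4.10) and 24% with d = 1.0 (inflation 1.25, SE 4.59).

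**4. Simulation of a T1 ANCOVA.** Settings: true total effect −11.5, T0–T1 correlation 0.5, d = 0.5, 100 per arm, 3,000 runs per scenario. Adding balance left the estimate at about −11.6 when m = 0, moved it from −11.5 to −5.8 when m = 0.5, and moved it from −11.6 to about 0 when m = 1.

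An unmeasured severity factor was then added, with assumed correlation 0.5 with balance and 10 units of hyaluronan per SD. With no mediation at all, adding balance moved the estimate from −11.4 to −8.9.

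**5. Simulation of the mixed model.** Random-intercept models, complete data at two times, 40 runs per scenario. Time-by-group estimate:

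| m | No balance term | Balance constant over time | Balance time-varying |
|---|---|---|---|
| 0.5 | −10.96 | −10.96 | −5.89 |
| 1 | −10.87 | −10.87 | +0.54 |

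The gap between about −10.9 and −11.5 is simulation error: 4.10/√40 ≈ 0.65. A constant term does nothing to the interaction. A time-varying term removes the mediated part.

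**The case against.** A reader might infer that the sub-study's primary hyaluronan comparison is adjusted for fluid balance, that its effect is adjusted away, and that power falls from 80% to 29%. The documents do not support that.

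- The primary outcome and its model list only T0, cancer stratum and site. The later list includes treating centre, which would be redundant where trial site is already a fixed effect. This favours reading the list as belonging to the pattern models.
- The values 11.5, SD 29 and 200 patients were planned for the T1 comparison. No power is planned for the pattern models, so no loss of power is shown for the analyses that the sentence most plausibly describes.
- Only the part acting through fluid is removed. The background itself calls the contribution of fluid therapy to glycocalyx degradation uncertain. The 29% is one point on an assumed range.
- A balance term constant over time leaves the time-by-group estimate, the test the plan names, unchanged.
- Bias through severity is possible, not certain.
- The sub-study also hopes to shed light on mechanism, for which a fluid-adjusted model could have a use.

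All of this stands, and it limits the claim. It does not remove it. The pattern models are still randomised comparisons, and the covariate is added without condition or label. A cumulative quantity measured across several sampling times is most naturally entered as time-varying. An interest in mechanism calls for a separately labelled mediation analysis with its own assumptions.

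**Conclusion.** The concern holds in limited form. The sub-study plans to put a consequence of the intervention into its between-group biomarker models and does not clearly exempt hyaluronan. Where the term is time-varying, or enters a T1 comparison, the group term no longer estimates the total effect set out as the aim, and bias from unmeasured severity becomes possible.

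The size cannot be fixed from the documents, because neither the mediated share nor the separation in fluid balance is given. The power figures are an illustration on the T1 planning values, not a prediction for any analysis as written. The simulated severity bias rests on assumed strengths.

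The issue is confined to this sub-study. The main trial's primary analysis adjusts only for site and cancer stratum (SAP, Statistical analyses, Primary outcome). The change is worth making because it is small and the choice of form should not wait until data are seen.

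**What to change.** In section 14.8.1.a:

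1. Delete cumulative fluid balance from the covariates of every model used to estimate or test the randomised group effect.
2. State that the primary T1 hyaluronan model uses T0, cancer stratum and site only. T0 should be described as what it is: a sample taken within an hour after enrolment, which the text does not show to precede randomisation.
3. Require any added severity or comorbidity covariate to use values from before randomisation. The sub-study does not say when SAPS 3 is scored, and it is not among the baseline variables in Protocol section 9.2.2. The SMS-ICU, which the main trial takes from the 24 hours before randomisation (Appendix 6), is an available alternative.
4. Keep fluid balance only in the association analyses, described as observational, or in a model labelled exploratory mediation, with its time window and form stated.

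The cost is a few sentences in the sub-study protocol. Removing the covariate needs no new data and does not change the sample size.

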A systematic review from 2016 by Vincent JL et al., which included 34 observational sepsis studies, showed that decrease in lactate concentration over time was consistently associated with lower mortality rates in all subgroups of patients (3). Hyperlactatemia is in clinical practice often thought to indicate that the human body is unable to uphold aerobic metabolism, due to tissue hypoxia and/or a deranged micro-circulation. This is often taken as an indication that a sufficient amount of resuscitation fluid has not yet been given to the patient. However, there are many other causes for hyperlactatemia, such as increased glycolysis, decreased clearance, and adrenergic stress response (4, 5).

In a Dutch multicenter randomized controlled trial from 2010 lactate-guided therapy in hyperlactatemia (albeit from various causes) reduced mortality, but interestingly the lactate levels did not differ significantly between the groups (6).

The current paradigm states that treatment with fluids decreases elevated concentrations of plasma lactate. Therefore, it is somewhat surprising that the post-hoc analysis of the Conservative versus Liberal Approach to fluid therapy of Septic Shock in Intensive Care (CLASSIC) feasibility trial (7)

The CLASSIC trial protocol Page 72/82

¹ Perioperative Medicine & Intensive Care, Karolinska University Hospital Huddinge, Sweden

² Department of Intensive Care, Rigshospitalet, University of Copenhagen, Copenhagen, Denmark.

³ Department of Anesthesia and Intensive care Medicine, Charles University Hospital Pilsen, Czech Republic

⁴ Department of Clinical Science and Education, Södersjukhuset, Karolinska Institutet, Stockholm, Sweden

showed no significant differences in plasma lactate levels between the two treatment groups even though there was >1 L difference in received fluids between the groups. The trial itself was not powered to investigate this outcome, but the finding is worth investigating in the main study.

Trial hypotheses and outcomes

The objective of this sub-study of the CLASSIC-trial is to use the randomization to either restrictive or standard fluid therapy to study temporal changes of lactate and time to normalization in patients with septic shock.

Research questions:

- 1. Does the lactate values differ between the two intervention groups in terms of
- a. Temporal changes in concentrations over time (based on all available plasma lactate analyses during the first 72 hours).
- b. Differences in delta-values (ΔLactate/h) over time (Calculated according to the method described under method & design).
- c. Differences in time to normalization (<2 mM/L) or discharge/death.
- 2. Same question(s) as above but comparing the cohort of patients with a higher baseline lactate (>4 mmol/L) in the two treatment arms.

Hypotheses:

- 1. Restrictive fluid therapy will neither significantly affect the delta-lactate nor time to normalization in patients treated for septic shock compared with standard (more liberal) fluid therapy
- 2. Patients in septic shock with a higher baseline lactate >4mmol/L will not decrease lactate levels faster with standard fluid therapy compared with restrictive fluid therapy. This is a sub-group analysis of 1).
- 3. A high baseline lactate and/or a low Δ Lactate/h is associated with a higher mortality irrespective of fluid treatment.

Outcome measure(s)

- 1. Primary outcomes are the differences in plasma lactate concentrations and Δ Lactate/h during the first 72 hours between the two treatment arms in the CLASSIC trial.
- 2. Secondary outcomes are the time to normalization of lactate, length of intensive care unit (ICU) stay and 90-day mortality in restrictive vs standard group of the CLASSIC trial.

The CLASSIC trial protocol Page 73/82

Method and design

All retrospective serial time-stamped point-of-care blood gas analyses from patients included in the CLASSIC trial will be collected and analyzed for the first 72 hours or until death or discharge from the ICU (depending on the availability from the centers).

Baseline characteristics (age, sex, body weight, pre-existing conditions and lab), daily fluid balance, urine output, treatment (mechanical ventilation, renal replacement therapy, vasopressors) and 90-day mortality data of included patients will be available from the CLASSIC trial database.

Normally distributed continuous data will be presented as mean +/- standard deviation and independent Student's t test will be used to compare means. Mann-Whitney U test will be used to compare mean ranks between groups if data shows non-normality assessed by the Shapiro-Wilk test. Such data will be presented as median (interquartile range). Data of categorical variables will be analyzed with Chi-square or Fisher's exact test as appropriate. A P-value of <0,05 will be considered as a statistically significant difference between groups for the primary outcomes.

ΔLactate/h is defined as (baseline lactate/baseline lactate – subsequent lactate) / baseline lactate x (100 / time interval(h)). Baseline lactate value is the lactate concentration at the time of randomization (from the electronic case report form). We will compare the groups using a mixed model for repeated measures to deal with missing values. Logistic multiple regression analysis for baseline lactate, ΔLactate/h and mortality adjusted for allocation treatment group and important risk factors (age, co-morbidities, severity of disease et cetera).

Centers will provide data in pseudonymized form. Data will be stored in an encrypted hard drive. Key for decryption and identification will be stored in a fire safe locked cabinet.

Sample size estimate

The Swedish centers have to date included 130 patients. Outside of Sweden the two hospital regions of Zealand, Denmark have included 604 patients and the University Hospital of Pilsen, Czech Republic, have included 50 patients. The estimated sample size will all together consist of 784 patients. The number of blood gas analyses will vary depending on patient and including center.

References:

- 1. Singer M et al (2016) The Third Inter- national Consensus definitions for sepsis and septic shock (Sepsis-3). JAMA 315(8):801–810
- 2. Evans L et al, Surviving sepsis campaign: international guidelines for management of sepsis and septic shock 2021, Intensive Care Medicine (2021) 47:1181–1247

The CLASSIC trial protocol Page 74/82

- 3. Vincent JL et al, The value of blood lactate kinetics in critically ill patients: a systematic review. Crit Care 2016:20;257
- 4. Hernandez G et al, The ten pitfalls of lactate clearance in sepsis, Intensive Care Medicine (2019) 45: 82-85
- 5. Garcia-Alvarez et al, Sepsis-associated hyperlactatemia, Critical Care 2014, 18:503
- 6. Jansen TC et al, LACTATE study group. Early lactate guide-therapy in intensive care unit patients: a multicenter, open-label, randomized controlled trial. Am J Respir Crit Care Med 2010;182:752-761.
- 7. Hjortrup et al, Effects of Fluid Restriction on measures of circulatory efficacy in adults with septic shock. Acta Anaesthesiol Scand 2017 Apr;61(4):390-398

The CLASSIC trial protocol Page 75/82

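### The lactate sub-study words time to normalisation in two ways and gives no rule for patients who die or leave the ICU first; analysed as research question 1c is worded, death counts the same as recovery

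*Protocol*

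**What the plan says.** All of the relevant text is in Protocol Appendix 8, section 14.8.1.b. The SAP does not cover this sub-study.

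- **Research question 1c:** "Differences in time to normalization (<2 mM/L) or discharge/death". Question 2 repeats the same questions in patients with baseline lactate above 4 mmol/L.
- **Hypothesis 1:** "Restrictive fluid therapy will neither significantly affect the delta-lactate nor time to normalization in patients treated for septic shock". Death and discharge are not mentioned, nor are they in the sub-study's stated objective.
- **Outcome list:** "Secondary outcomes are the time to normalization of lactate, length of intensive care unit (ICU) stay and 90-day mortality". Normalisation stands alone, and mortality is a separate item.
- **Data window:** blood gases "will be collected and analyzed for the first 72 hours or until death or discharge from the ICU", subject to what each centre can supply.
- **Methods:** t test for normally distributed data; otherwise "Mann-Whitney U test will be used to compare mean ranks between groups if data shows non-normality assessed by the Shapiro-Wilk test". Chi-square or Fisher's exact test is named for categorical data and logistic regression for mortality. For repeated values: "We will compare the groups using a mixed model for repeated measures to deal with missing values".
- **Significance:** "A P-value of <0,05 will be considered as a statistically significant difference between groups for the primary outcomes". Time to normalisation is a secondary outcome, so this rule does not cover it.

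**The concern.** Taken literally, 1c is a composite: the clock stops at normalisation, at discharge or at death, whichever comes first. A patient whose lactate normalises at 20 h and a patient who dies at 20 h would contribute the same value. An arm with more early deaths would then have shorter times and could be read as clearing lactate faster.

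The rest of the sub-study text does not settle the matter. The outcome list leaves death and discharge out of the event but does not say what value or status a patient has who dies or leaves without normalising. Blood-gas collection ends at death, ICU discharge or 72 h, so every patient who has not normalised by then needs a rule. A Mann-Whitney comparison of times needs a number for each patient, and for a patient who dies the only one that the text suggests is the time of death.

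The gap matters because early death is unlikely to be independent of lactate. The sub-study's background links falling lactate to lower mortality, and its third hypothesis rests on that link. Time to normalisation is part of the sub-study's objective and of hypothesis 1, so it will be reported.

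**Working it through.** **The plan's own figure.** The sub-study sample size is a sum of available patients: 130 (Sweden) + 604 (Zealand) + 50 (Pilsen) = 784, as stated. With 1:1 allocation that is about 392 per arm. No power, event count or effect size is given for time to normalisation.

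**Inputs that are assumed.** The documents give 45% mortality at day 90 under standard care, but no 72-hour rate of death, discharge or normalisation. All 72-hour rates below are assumptions.

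**1. Composite as worded, death only.** Hazards are constant and the normalisation hazard is the same in both arms. Each percentage fixes its own hazard, ignoring the other event.

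- Normalisation, 60% by 72 h: h = −ln(0.40)/72, so 72h = 0.916.
- Death: 72g = −ln(0.90) = 0.105 for 10%; −ln(0.85) = 0.163 for 15%; −ln(0.80) = 0.223 for 20%.
- Pooled hazard ratio = (h + g₂)/(h + g₁).
- 10% vs 15%: (0.916 + 0.163)/(0.916 + 0.105) = **1.056**.
- 10% vs 20%: (0.916 + 0.223)/(0.916 + 0.105) = **1.115**.

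Both favour the arm with more deaths, although normalisation is identical by construction.

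**2. Composite with discharge included.** The percentages are now actual first-event proportions at 72 h in the reference arm: 60% normalised, 10% dead, 5% discharged before normalising. The total hazard is H = −ln(0.25)/72, so 72H = 1.386, split 0.800 : 0.133 : 0.067. In the other arm only the death hazard is doubled.

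- Composite hazard ratio = 0.800 + 2 × 0.133 + 0.067 = 1.13.
- Median composite time = ln 2/H: 36.0 h falls to 31.8 h, which looks faster.
- Cumulative incidence of normalisation = (0.800/1.133) × (1 − exp(−1.386 × 1.133)) = 55.9%, against 60.0% in the reference arm. Fewer patients normalise.
- Break-even: an arm with a normalisation hazard ratio as low as 1 − 0.133/0.800 = 0.83 would still look no slower.

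**3. Range.** With 60% normalised and 5% discharged, reference deaths of 5% to 15% and a death hazard multiplied by 1.25 to 3, the composite hazard ratio runs from 1.02 to 1.38, and the incidence of normalisation falls in every case. Results for reference deaths of 10% (log-rank test, 392 per arm):

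| Dead at 72 h | Composite HR | Chance of p<0.05 |
|---|---|---|
| 10.0% vs 12.3% | 1.03 | about 6% |
| 10.0% vs 18.6% | 1.13 | 34% |
| 10.0% vs 26.1% | 1.27 | 84% |

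**4. Censoring instead.** Use the same setting as step 2, with death and discharge censored and independent of normalisation.

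- The cause-specific hazard ratio for normalisation is 1.00, so the hazard comparison is not biased.
- One minus Kaplan-Meier at 72 h is 1 − exp(−0.800 × 1.386) = 67.0% in both arms, against true incidences of 60.0% and 55.9%. The probability is overstated in each arm.
- A simulation lets a shared severity factor raise the death hazard and lower the normalisation hazard, so that deaths are informative. At double the death hazard the crude normalisation rate ratio is 1.02, and at triple 1.03. A between-arm bias then appears, but a small one under these assumptions. In the same simulation at double the death hazard, the composite rate ratio is 1.12 and the incidence of normalisation falls from 68.0% to 64.4%.

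**The case against.** The strongest reply is that the added words occur in one research question only. The objective, hypothesis 1 and the outcome list name normalisation alone, and data collection stops at death or ICU discharge, so 1c may simply mark the end of observation. This stands. A reader might infer that the sub-study has settled on a pooled endpoint, but the documents do not support that. They show two wordings and no rule for choosing between them.

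A reader might also infer that the arm with more deaths is favoured whichever reading is taken. That is not supported either. With independent hazards, censoring at death leaves the cause-specific hazard ratio at 1.00. The absolute probability of normalisation is overstated, which is a different fault. Bias between arms under censoring needs deaths that are both informative and unequal.

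Other points against it also hold:

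- The size rests wholly on assumed 72-hour rates, and no difference in early mortality is established.
- Discharge could add to the effect or offset it.
- Hazard ratios and Kaplan-Meier curves are not planned methods here.
- Mortality at 90 days is listed separately, so a marked excess of deaths would probably be noticed.

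None of this supplies the missing rule for patients who die or leave before normalising.

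**Conclusion.** The point holds as an inconsistency and an omission: 1c conflicts with the outcome list, and the handling of death and ICU discharge before normalisation is undefined. If 1c is followed as worded, the direction of the error is known. With equal normalisation and discharge hazards, the arm with more early deaths looks faster, by a hazard ratio of about 1.06 (10% vs 15% dead by 72 h) to 1.12 (10% vs 20%). These figures assume constant hazards and 60% normalisation by 72 h. If early deaths are similar, the effect is negligible.

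This is a secondary outcome of a sub-study. The sub-study's primary outcomes (lactate concentration and its hourly change) have their own analysis, and the main trial's primary analysis is not touched. The change is worth making because it is cheap and because, as worded, an excess of early deaths could be reported as faster recovery.

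**What to change.** 1. Reword research question 1c to match the outcome list: time to normalisation of lactate.
2. Define the event as the first lactate below 2 mmol/L (the sub-study's own threshold) within 72 h of randomisation, with administrative censoring at 72 h.
3. Treat death before normalisation as a competing event. Treat ICU discharge before normalisation as a separate competing event, because censoring at discharge is itself likely to be informative. Give an analysis that censors at discharge as a sensitivity analysis.
4. Report the cumulative incidence of normalisation by arm, cause-specific hazard ratios, and deaths by 72 h as a separate line. Apply the same rules to the subgroup with baseline lactate above 4 mmol/L.

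**Cost.** The change needs a short amendment to the sub-study text and slightly more analysis work, using standard methods. The practical burden is timing. The data listed in Protocol 9.2.2 include a date of death but no clock time for death or ICU discharge, so centres would have to supply those times with the blood-gas files wherever the main database holds only dates.
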